2 STUDY OBJECTIVES

The primary objective of this study is:

• Evaluation of $\alpha_v \beta_6$ receptor occupancy by PLN-74809 in the lungs, as assessed by changes from baseline in $\alpha_v \beta_6$ PET tracer uptake patterns following a single dose.

The secondary objective is:

• Assessment of the safety and tolerability of PLN-74809 in IPF participants

The exploratory objective is:

•

Confidential Page 294 of 331

3 INVESTIGATIONAL PLAN

3.1 Overall Study Design and Plan

| This study is an open-label study in which up to 12 participant | ts with IPF will receive up to |
|---|----------------------------------|
| two doses of PLN-74809, starting at 60 mg | or 80 mg |
| Higher planned doses, including 120 mg, 240 mg | g, and 320 mg, will also be |
| evaluated | |
| All participants will undergo PET imagi | ing at the Baseline Visit and or |
| the day of PLN-74809 dosing. | |

Eligible participants consenting to receive a maximum of 4 different doses of PLN-74809 (e.g., 60 mg and 120 mg) will need to undergo a ≥14-day washout between doses, and not have to repeat Baseline PET imaging. Additionally, if in the opinion of the Investigator, there is no clinical decline, the other Screening and Baseline procedures do not have to be repeated. If the PET ligand cannot be successfully synthetized on the scheduled day, participants will wait at least 1 week before another dose of PLN-74809 is administered.

All PET imaging will be performed using the R_01 Knottin tracer, as generated by the radiology department at Stanford Medical Center. Post-dose PET imaging, for the assessment of $\alpha_v \beta_6$ receptor occupancy, will be performed to coincide with PLN-74809 time to maximum observed drug concentration (T_{max} ; ~4 hours after the administration of study drug). Participants will undergo no more than 3 PET imaging scans (Baseline and up to 2 scans post PLN-74809 dosing).

Blood samples for PLN-74809 PK will be obtained before and at 0.5, 1, 2, 3, and 4 hours after dosing on Day 1 and at 24 hours after dosing (Day 2).

[figure not shown]
Forced vital capacity (FVC) will be performed on all participants at Screening for inclusion/exclusion purposes.

Except for the previously described periods, participants will be allowed to return to their homes between study visits.

3.2 Rationale for Study Design and Control Group

Confidential Page 295 of 331

Confidential Page 296 of 331

3.4 Study Duration and Dates

Screening for all participants will be performed up to 35 days prior to dosing (dosing will be on Day 1). The Baseline Visit (including PET) will be performed on Day -7 to allow for washout of the PET ligand between PET procedures. Screening & Baseline visit may occur on the same day, if appropriate.

Participants will receive PLN-74809 on Day 1 and will attend a Follow-Up Visit 7 days (±2 days) after administration of the single dose. The study duration will be approximately 43 days for participants testing 1 dose of PLN-74809.

For participants consenting to receive up to four single doses of PLN-74809, at least 14 days will be added to the study duration due to the required washout period. Refer to Section 5.5 for further information.

Confidential Page 297 of 331

4 STUDY POPULATION

4.1 Inclusion Criteria

Each participant must meet the following criteria to be enrolled in this study:

- 1. Participants aged 40 or older.
- 2. Confident diagnosis of IPF, within 8 years prior to Screening, according to the Fleischner Guidelines criteria; specifically either HRCT imaging showing a pattern of typical or probable usual interstitial pneumonia (UIP) or a histopathology specimen demonstrating a UIP pattern in the correct clinical context (and confirmed by multidisciplinary conference review at study site.
- 3. FVC percent of predicted ≥ 45%; historical FVC for entry in the study is permitted if within 1 month of screening.
- 4. Diffusing capacity for carbon monoxide (DLco) (hemoglobin-adjusted) ≥30%; historical DLco for entry in the study is permitted if within 1 month of screening.
- 5. Participants currently receiving treatment for IPF with nintedanib or pirfenidone are allowed, provided these drugs have been given at a stable dose for at least 3 months before the Screening Visit and are expected to remain unchanged during the study.
- 6. Female participants of nonchildbearing potential must be either surgically sterile (hysterectomy, bilateral tubal ligation, salpingectomy, and/or bilateral oophorectomy at least 26 weeks before the Screening Visit) or postmenopausal, defined as spontaneous amenorrhea for at least 2 years.
- 7. Female participants must have a negative pregnancy test at Baseline.
- 8. Female participants of childbearing potential (i.e., ovulating or premenopausal and not surgically sterile) and all male participants with sexual partners of childbearing potential must agree to use highly effective methods of birth control during their participation in the study and for 30 and 90 days, respectively, after the last administration of study drug. Hormonal contraceptives are not allowed. Highly effective methods of birth control are defined as those with 99% or greater efficacy
- 9. Participants must agree to abstain from sperm or egg donation through 90 or 30 days, respectively, after administration of the last dose of study drug.
- 10. Able to understand the purpose of the study and its procedures and to sign a written informed consent form.

[figure not shown]
Confidential Page 298 of 331

Pliant Therapeutics Inc.
Page 24

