5.8.4 Contraception

Female participants of childbearing potential (i.e., ovulating or premenopausal and not surgically sterile) and all male participants with sexual partners of childbearing potential must use highly effective methods of birth control during their participation in the study and for 90 days after the last administration of study drug. Highly effective methods of birth control are defined as those with 99% or greater efficacy

Acceptable methods of contraception for female and male participants enrolled in the study include the following:

- Complete abstinence from sexual intercourse if this is the participant's usual and preferred lifestyle
- Implanted contraceptives
- Oral hormonal contraceptives if using for 1 year or more
- Dual method of contraception:
 - o Condom in conjunction with use of an intrauterine device
 - o Condom in conjunction with use of a diaphragm
 - Oral hormonal contraceptives with less than 1 year of use in conjunction with condom
- Sexual partner with surgical sterilization (e.g., vasectomy, tubal ligation, hysterectomy and/or bilateral oophorectomy).

Females who are using hormonal contraceptives should have started use at least 12 weeks before Screening.

Participants must agree to abstain from egg or sperm donation and to continue condom use through 30 or 90 days, respectively, after administration of the last dose of study drug.

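### Section 4.1 criterion 8 and Section 5.8.4 give women of childbearing potential conflicting rules on hormonal contraceptives and on the post-dose contraception period (30 versus 90 days)

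*Protocol*

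**What the plan says.** Protocol Section 4.1, criterion 8, applies to female participants of childbearing potential and to male participants whose partners are of childbearing potential. It requires highly effective birth control during the study and "for 30 and 90 days, respectively, after the last administration of study drug", that is, 30 days for women and 90 for men. It then adds "Hormonal contraceptives are not allowed". Synopsis criterion 8 gives the same 30/90-day split. The ban does not appear in its visible text.

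Protocol Section 5.8.4 addresses the same two groups and requires "birth control during their participation in the study and for 90 days after the last administration of study drug", with no split by sex. Its list of acceptable methods, introduced as applying to female and male participants, includes:

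- "Oral hormonal contraceptives if using for 1 year or more"
- "Oral hormonal contraceptives with less than 1 year of use in conjunction with condom", as one of the dual methods
- "Implanted contraceptives", without saying whether hormonal implants are meant

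It continues: "Females who are using hormonal contraceptives should have started use at least 12 weeks before Screening". Its closing sentence reads "Participants must agree to abstain from egg or sperm donation and to continue condom use through 30 or 90 days, respectively", counted from the last dose.

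**The concern.** The ban in criterion 8 and the list in 5.8.4 cannot both be the intended rule. A woman who has taken an oral contraceptive for more than a year fails an inclusion criterion and at the same time uses a method that the protocol lists as acceptable. The medication review before enrolment (Section 5.7) should bring the drug to light, but whoever does that review then finds it barred in one section and accepted in another.

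The period has the same problem. A woman may agree to 30 days on the strength of criterion 8, while the restrictions section asks for 90.

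At stake are eligibility and pregnancy prevention in a trial of an investigational drug: a possible eligibility deviation in one direction, an unnecessary refusal in the other, and unclear instructions on how long to continue contraception.

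**Working it through.** No sample-size or power calculation applies. The check sets the current texts side by side.

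| Item | 4.1, criterion 8 | 5.8.4 |
|---|---|---|
| Hormonal methods | Barred | Two oral hormonal options accepted |
| Condition for hormonal users | None, since barred | Started at least 12 weeks before Screening |
| Post-dose period, women | 30 days | 90 days (first sentence) |
| Post-dose period, men | 90 days | 90 days |

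**Methods.** Section 5.8.4 lists seven options: abstinence; implanted contraceptives; oral hormonal for a year or more; condom with intrauterine device; condom with diaphragm; oral hormonal for under a year with condom; sterilized partner. Two are expressly hormonal and conflict with the ban. One (implanted) conflicts if it covers hormonal products. The other four are not expressly hormonal: 2 + 1 + 4 = 7. The 12-week sentence also has no place under a ban, because it presupposes that hormonal users enter the study.

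**Period for women.** 90 − 30 = 60 days. Thirty days is stated as the birth-control period in two places (synopsis criterion 8 and 4.1 criterion 8, which are two copies of one criterion). Ninety days is stated in one (first sentence of 5.8.4). The men's period agrees throughout.

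**Readings that might reconcile the texts.**
- *Missing text.* The definition of highly effective methods appears cut short in the synopsis, 4.1 and 5.8.4. The sentences that conflict are complete, so this does not explain the conflict.
- *Hormonal options meant only for partners of male participants.* The list is stated to cover female and male participants, and the 12-week rule is tied to Screening, which participants undergo. The ban is not limited to one sex either.
- *Pregnancy reporting settles the period.* Section 6.10.6 has pregnancies reported up to 90 days after the last dose. That governs reporting, not how long contraception is required.

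**The case against.** The best reply is that the stricter text can always be followed. Section 4.1 says that every criterion must be met for enrolment, and Section 10.7 repeats that eligibility requirements must be met. On that view an oral contraceptive user is simply ineligible, and a later list of restrictions cannot admit her. Likewise, 90 days of contraception also meets a 30-day requirement. This stands as far as it goes: neither conflict forces the site into a breach. But it supplies a rule of precedence that the protocol does not state, and it leaves the 12-week sentence without a purpose.

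The reply is also right that the effect is slight. One center is named, so there is no divergence between sites. There is a Baseline pregnancy test, medications are reviewed before enrolment, and pregnancies are reported to 90 days.

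Two stronger readings are tempting, and the documents do not support them:

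- A reader might take the closing sentence of 5.8.4 as a third statement of 30 days for women, and so as a flat contradiction within that section. It concerns egg or sperm donation and continued condom use. How the 30/90 split maps onto the condom clause is unclear, and a woman relying on abstinence or an implant gets no shorter period from it. It is ambiguous beside the 90-day rule, but it is not a separate overall contraception period.
- A reader might stress that days 31 to 90 fall after the last scheduled visit, which is 7 ± 2, or 5 to 9, days after dosing. Most of the 30-day period does too: between 30 − 9 = 21 and 30 − 5 = 25 of its days. Visit timing does not separate the two rules.

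**Conclusion.** The inconsistency is real and lies in the current protocol text, on two points: whether hormonal contraceptives are allowed, and whether women continue contraception for 30 or 90 days. The condom clause in 5.8.4 adds an ambiguity, nothing more.

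The point is minor, an improvement the sponsor could make. At most 12 participants aged 40 or older are planned. The documents do not say how many would be women of childbearing potential, so few or none may be affected. No endpoint, sample size or analysis changes.

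Two things could not be checked. The consent form was not available and may already state one rule. Synopsis criterion 8 appears cut short, so the absence of the ban from its visible text is not proof that it was left out. The visible text gives no reason for the ban, so the documents do not show which of the two rules was intended.

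**What to change.** Adopt one rule and state it identically in the synopsis, 4.1, 5.8.4 and the consent form.

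**Hormonal methods**
- If the ban stands: delete the two oral hormonal options and the 12-week sentence from 5.8.4, limit the implanted option to non-hormonal products or remove it, and make sure synopsis criterion 8 carries the ban.
- If the ban is not intended: delete it from criterion 8 in 4.1.

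**Post-dose period for women**
- Either 90 days, the stricter period, which satisfies both texts: change criterion 8 in the synopsis and in 4.1, and separate the condom clause from the donation clause in 5.8.4 so that it also reads 90 days. The sponsor should then confirm whether the 30-day egg-donation period should match.
- Or 30 days: give the first sentence of 5.8.4 the same split as criterion 8 (30 days for women, 90 for men).

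The 90-day pregnancy reporting window in Section 6.10.6 can stay in either case.

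The cost is wording at the next amendment and a check of the consent form. Visits, sample size and analyses are unchanged.

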4.2 Exclusion Criteria

Participants who meet any of the following criteria will be excluded from the study.

- 1. Hypersensitivity to PLN-74809 or to any of the excipients to PLN-74809.
- 2. Not a suitable candidate or unlikely to comply with study requirements, in the opinion of the Investigator.
- 3. Currently receiving or planning to initiate treatment for IPF (fibrosis) during the study with pharmacological agents not approved for that indication by the Food and Drug Administration (FDA).
- 4. Forced expiratory volume during the first seconds of the forced breath (FEV1)/FVC ratio <0.7.
- 5. Suspicion of an interstitial lung disease (ILD) different from IPF according to the Investigator.
- 6. Clinical evidence of active infection, including but not limited to bronchitis, pneumonia, sinusitis that can affect FVC measurement or IPF progression.
- 7. Any other condition that prevents the correct assessment of spirometry performance (e.g., a broken rib or chest pain of other origin that prevent adequate forced breathing).
- 8. Known acute IPF exacerbation or suspicion by the Investigator of such within 6 months of Screening.
- 9. Smoking of any kind (not limited to tobacco) within 3 months prior to Screening, as documented in the medical history, or unwilling to avoid smoking throughout the study.
- 10. Any ongoing known malignancy, except for localized cancers (e.g., basal cell carcinoma).

- 14. Any medical condition that, in the opinion of the Investigator, may make the candidate not suitable for the study.
- 15. History of anaphylaxis to intravenous (IV) drugs.
- 16. Any of the following liver function test criteria above specified limits: total bilirubin >1.5× the upper limit of normal (ULN); aspartate aminotransferase (AST) or alanine aminotransferase (ALT) >3× ULN; alkaline phosphatase >2.5× ULN.

[figure not shown]
Confidential Page 299 of 331

- 17. Hemoglobin <10.0 g/dL at Screening.
- 18. Pregnant or lactating females.
- 19. Medical or surgical condition known to affect drug absorption.
- 20. Participation in a clinical trial with an investigational agent in the 30 days prior to Screening apart from PLN-74809.

Confidential Page 300 of 331

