5.7 Concomitant Therapy

Treatment with current standard of care (nintedanib or pirfenidone) for IPF is allowed provided these drugs have been given at a stable dose for at least 3 months before initiation of Screening and are expected to remain unchanged during the study.

Treatment for IPF (fibrosis) with any other non-FDA-approved agent is not permitted during the study. Treatments to address IPF disease symptoms, (cough, gastroesophageal reflux disease, etc) are allowed.

Confidential Page 302 of 331

Treatment with another investigational drug, investigational device, or approved therapy for investigational use within 30 days or 5 half-lives (whichever is longer) before anticipated dosing is prohibited apart from PLN-74809.

Other medications to provide reasonable patient care of IPF or other comorbidities are allowed during the study; however, these should only be used if necessary because, at this stage of development, no formal drug-drug interaction studies with PLN-74809 have been performed.

During screening, all medications, including over-the-counter medications and herbal supplements, taken during the 30 days prior to Screening will be recorded and reviewed by the Principal Investigator (PI) in consultation with the Medical Monitor to determine whether the participant is suitable for inclusion. For other concomitant medications that are needed during the study conduct, the PI should consult with the Medical Monitor as soon as feasible.

If used, all concomitant medications, including both prescription and nonprescription drugs, should first be discussed with the PI and Medical Monitor before administration. This requirement does not apply in the case of urgent, necessary treatment of adverse events (AEs). In all cases, all medications, including over-the-counter medications and herbal supplements, that are taken by participants during the course of the study will be recorded using the generic name of the medication. In addition, for participants who are receiving nintedanib or pirfenidone, the time of drug administration should be collected on each day on which samples are obtained for assessing PLN-74809 PK.

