5.8 Restrictions

5.8.1 Prior Therapy

Previous use of IPF standard-of-care treatment (pirfenidone or nintedanib) is allowed for participation in this study. Prohibited medications (see Section 5.7, Concomitant Therapy) should be stopped at least 5 half-lives before dosing on Day 1.

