- An HRCT at Screening may not be needed if a scan that weeks the quality necessary for diagnosis purposes exists. If an HRCT is performed at Screening, a second one is not needed during PET. An HRCT during PET may be performed if the Screening HRCT is not adequate for the assessment of HRCT-PET relationship.
- g PET to be performed at least 4 hours post-dose and no more than 30 minutes after the 4 hour PK timepoint.
- b Blood samples for radiotracer PK to be taken 1, 3, 5, 10, 30, and 60 minutes after completion of radiotracer injection for PET-CT. Each collection time point has a +4-min window. Refer to the Radiology Manual for details of sample collection including definitive information about allowable windows.
- Dosing to occur in connection to PET synthesis and availability.
- Day 2 plasma PK sample to be collected 24 hours post-dose.
- Adverse events and concomitant medications to be collected at each visit.
- For participants testing 2 different doses of PLN-74809, the Baseline PET scan will be based on the first single dose screening and not repeated. Additionally, if in the opinion of the Investigator, there is no clinical decline, the other Screening and Baseline procedures do not have to be repeated. Participants must washout of PLN-74809 for at least 14 days prior to testing the second dose level of PLN-74809.
- ⁿ Screening & Baseline visit may occur on the same day, duplicative assessments will not need to be repeated
- Hematology and clinical chemistry may be conducted outside of study institution for EOS visit, if appropriate.

Confidential Page 326 of 331

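### Both readable pre-study washouts exempt PLN-74809, and no readable text sets an interval between PLN-74809 taken in another study and the Baseline PET

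*Protocol*

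**What the plan says.** Two restrictions in the protocol act before the study, and both exempt the study drug. Exclusion 20 in Section 4.2 rules out "Participation in a clinical trial with an investigational agent in the 30 days prior to Screening apart from PLN-74809"; the synopsis version has the same exception. Section 5.7 says that treatment with another investigational product "within 30 days or 5 half-lives (whichever is longer) before anticipated dosing is prohibited apart from PLN-74809".

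Three other provisions come close:

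- Section 5.8.1 says that prohibited medications "should be stopped at least 5 half-lives before dosing on Day 1", but refers to Section 5.7 for what is prohibited.
- Exclusion 3 bars anyone "Currently receiving or planning to initiate treatment for IPF (fibrosis) during the study with pharmacological agents not approved for that indication". It has no PLN-74809 exception, but it concerns current or planned treatment and gives no time since a last dose.
- Section 5.7 has the investigator and Medical Monitor review all medication from the 30 days before Screening. It gives no PLN-74809 criterion.

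The readable intervals for PLN-74809 itself lie between doses in this study. Appendix 1 states: "Participants must washout of PLN-74809 for at least 14 days prior to testing the second dose level of PLN-74809". Re-dosing after a failed tracer synthesis requires at least one week.

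On the Baseline scan, Section 3.4 says: "The Baseline Visit (including PET) will be performed on Day -7 to allow for washout of the PET ligand between PET procedures". It also says: "Screening & Baseline visit may occur on the same day, if appropriate". Section 2 defines the primary objective as occupancy "as assessed by changes from baseline in" tracer uptake. The Baseline scan is not repeated for later doses. Under Section 6.8 and Appendix 1, the first PLN-74809 plasma sample is the Day 1 pre-dose sample. SAP Section 6.2.3 defines baseline without reference to prior exposure, and SAP Section 1 leaves the PET analysis to a separate plan.

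**The concern.** The Baseline scan is the reference for the primary endpoint, so it should be free of study drug. Protocol Section 1 describes the tracer as competitive at the receptor, and Section 6.12 expects the drug to reduce tracer binding. Drug still on the receptor at Baseline would lower the reference uptake, so the post-dose fall would look smaller than it is.

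The contents list has headings for ongoing Phase 1 and Phase 2 studies of PLN-74809, so recent exposure elsewhere is conceivable. The exemption is an explicit provision, not a missing detail. Applied as written, it removes the only readable intervals that would otherwise separate earlier drug from this study. At stake is the occupancy estimate of any participant admitted in this way, and the summary of each dose to which that participant contributes.

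**Working it through.** The plan states no occupancy, half-life or power, so there is no figure to reproduce. The check is whether any readable rule closes the gap, and then which way and how far the bias could go.

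**Step 1. Does any readable rule separate earlier PLN-74809 from the Baseline PET?**

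| Provision | Effect on PLN-74809 from another study |
|---|---|
| Exclusion 20 (30 days before Screening) | Exempt |
| Section 5.7 (30 days or 5 half-lives before dosing) | Exempt |
| Section 5.8.1 (5 half-lives before Day 1) | Covers only what 5.7 prohibits; timed to Day 1, not to the scan |
| Exclusion 3 | Bars current treatment; no interval |
| 30-day medication review (5.7) | Case by case; no threshold |
| In-study washout and one-week wait | Apply only after the first in-study dose, hence after the Baseline scan |
| Baseline on Day -7 | Justified by tracer washout; Screening may be the same day |

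No readable row sets an interval.

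**Step 2. Direction.** Let R0 be occupancy at Baseline, R1 true post-dose occupancy, and f the displaceable share of uptake. The measured fractional fall is

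M = 1 − (1 − f·R1) / (1 − f·R0).

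With R0 = 0, M = f·R1. For any f above 0, raising R0 shrinks the denominator and M falls. The bias is therefore toward zero for every f above 0, as long as R0 does not exceed R1.

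**Step 3. Size for an assumed R0, with f = 1.**

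- R1 = 80%: 1 − 0.2/0.9 = 78%; 1 − 0.2/0.8 = 75%; 1 − 0.2/0.5 = 60%, for R0 of 10%, 20% and 50%.
- R1 = 50%: 1 − 0.5/0.8 = 37.5%; 1 − 0.5/0.7 = 29%, for R0 of 20% and 30%.

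With f = 0.5 and R1 = 70%, a clean Baseline gives a fall of 35.0%. R0 of 10%, 25% and 50% gives 31.6%, 25.7% and 13.3%.

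**Step 4. Dependence on the time since the last dose.** Assume that the earlier dose also reached 70% peak occupancy and that f = 1. The remaining drug fraction is x = 0.5^(gap/half-life), and R0 = r·x/(1 + r·x) with r = 0.7/0.3 = 2.333. For example, with a 24 h half-life and a 1-day gap, x = 0.5, R0 = 1.167/2.167 = 53.8%, and M = 1 − 0.300/0.4615 = 35.0%.

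| Assumed half-life | 1 day | 3 days | 7 days | 14 days |
|---|---|---|---|---|
| 24 h | 35.0% | 61.2% | 69.5% | 70.0% |
| 48 h | 20.5% | 45.3% | 63.8% | 69.5% |
| 72 h | 14.4% | 35.0% | 56.1% | 67.2% |

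Entries are the measured value when the truth is 70%. A very recent dose matters a great deal. At 14 days the largest loss in the table is 70.0 − 67.2 = 2.8 points.

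**Step 5. Would the schedule reveal it?** The Day 1 pre-dose sample comes 7 days after a Day -7 scan. Over those 7 days, drug present at the scan falls to 0.8%, 8.8% or 20% of its level for half-lives of 24, 48 or 72 h. SAP Section 6.10.1.1 reports values below 1.00 ng/mL as below quantification. The sample might or might not show earlier exposure.

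**Step 6. Reach.** Up to 12 participants with at most two post-dose scans give at most 24 scans over five dose labels, on average 24/5 = 4.8 per dose. In a group of five with a true 80%, one scan measured as 60% moves the mean to (4 × 80 + 60)/5 = 76%. Because Baseline is reused, the same participant can affect a second dose group.

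**The case against.** The strongest objection is that the case rests on a negative in redacted text. Exclusion criteria 11 to 13, synopsis criterion 21 and the content of Sections 5.3 to 5.5 cannot be read, and the separate PET analysis plan is not available. Any of these could deal with earlier PLN-74809. This stands. A reader might infer that someone dosed elsewhere the day before Screening is eligible. That cannot be concluded with at least three criteria unseen.

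A reader might also infer that PLN-74809 is free of every washout. It is not: the in-study washout of at least 14 days applies to it. Only the two readable pre-study restrictions exempt it.

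The exemption may have been written for participants returning for another dose in this study. Their Baseline scan precedes all in-study drug, so that reading causes no contamination. It is plausible, but the wording is not limited to it.

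Exclusion 3 and the 30-day medication review are real safeguards. They confine the issue to people who have stopped PLN-74809 and give the investigator and Medical Monitor a chance to notice. Neither supplies an interval. The ongoing studies are visible only as headings, and nothing readable shows that their participants could come to this single site.

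Finally, the study is exploratory with no hypothesis test, and a bias toward zero would not create false evidence of target engagement. It would still understate occupancy and blur the comparison between doses.

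**Conclusion.** The point holds in a conditional form. Exclusion 20 and Section 5.7 exempt PLN-74809 from both readable pre-study washouts, and no readable text keeps earlier PLN-74809 away from the Baseline PET. If a recently exposed participant enrols, measured occupancy is biased toward zero in each of that participant's post-dose scans.

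The direction rests on competition between drug and tracer, which the protocol states. The size rests on assumed half-life, residual occupancy and displaceable share. Under those assumptions it runs from under 1 point to more than 50 points on a true 70%, depending mainly on how recent the earlier dose was. The documents do not support saying that the trial's results are biased, because they do not show that any such participant was enrolled. Nor do they support saying that residual drug would necessarily go unseen.

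This lies between a point to consider and one that should be fixed. Confidence is medium because of the unreadable text.

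**What to change.** Reconcile exclusion 3, exclusion 20 (body and synopsis), Section 5.7 and the in-study washout so that the exemption does not extend to the Baseline PET. There are two ways to do this: limit it to re-dosing within this study, or limit it to candidates whose last earlier PLN-74809 dose precedes the Baseline PET by an interval that the sponsor sets and states. If the redacted text already holds such a rule, a cross-reference is enough.

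In addition:

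- Record the date and dose of any PLN-74809 taken before this study.
- For those participants, assay PLN-74809 in blood already drawn at Baseline.
- Flag Baseline scans with measurable drug, and state in the PET analysis plan that results will be reported with and without the affected participants.

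The cost is a short amendment, one extra assay for each such participant, and a wait before Baseline for a few candidates. If enrolment has closed, the exposure record and the with-and-without report remain feasible; scans can then be flagged from the recorded exposure, or from an assay where Baseline blood was kept.
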